To further investigate the impact of CBPDE, the following analyses will be performed:

- baseline characteristics by CBPDE (yes/no);

	Statistical Analysis Plan
	Sponsor: NOVARTIS Protocol number: CRLX030A3301

- concomitant medications by CBPDE (yes/no);
- worsening heart failure/all cause death through Day 5 by CBPDE (yes/no) and by CBPDE impact on study drug administration (dose decreased but not discontinued, or study drug discontinued, or both);
- adverse events through Day 5 and through Day 14 by CBPDE (yes/no)

Causes that lead to a re-hospitalization or emergency/urgent care >24 hours not resulting in admission

In case the reason for re-hospitalization or emergency/urgent care >24 hours not resulting in admission is HF, renal impairment, or cardiac (chest pain, ACS, MI), further details are collected in dedicated eCRF sections (“Rehospitalization information”, “Heart failure details”, “Acute MI/ACS/chest pain” and “Renal failure”).

Data will be summarized presenting absolute and relative frequencies (percentages calculated on events with non-missing information) for discrete variables; presenting number of observations, mean, standard deviation, median, first and third quartiles, minimum and maximum for continuous variables.

Survival and Death information

Descriptive statistics by treatment group will be presented for death information.

All deaths occurred will be listed with all their details.

Pregnancy test results

Any pregnancies reported will be listed and outcome reported.

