5.5.9 Discontinuation of study treatment

The investigator shall discontinue the study drug infusion for a patient if, on balance, he/she believes that continuation would be detrimental to the patient's well-being.

In particular, the study drug administration must be discontinued under the following circumstances:

- The patient's systolic BP falls to <100 mmHg in two consecutive measurements 15 min apart. Measures may be taken by the investigator to address the decrease in blood pressure during the intervening 15 minutes, if clinically indicated
- Pregnancy
- Any other protocol deviation that results in significant risk to the patient's safety

During the study drug infusion, administration of any cardiovascular IV therapies, including vasodilators (including nesiritide), positive inotropic agents and vasopressors, or mechanical support (intra-aortic balloon pump, endotracheal intubation, assisted ventilation, or any ventricular assist device) is allowed. The continuation or discontinuation of study drug infusion will then be at the discretion of the investigator.

Of note, patients who discontinue investigational treatment shall NOT be considered withdrawn from the study, and are required to be followed per the visit/assessment schedules illustrated in [Table 6-1](#) until the study is complete. The investigator must register the patient's discontinuation from the study and/or investigational treatment in the eCRF.

Patients can also refuse to participate in specific aspects of the study and/or take study medication at any time without withdrawing consent. Investigators shall make every effort to accommodate the needs of the patients to make it possible for them to continue to participate in the remaining aspects of the study. This includes performing telephone visits to obtain vital status and/mortality information for patients who are unable to or refuse to return for clinic visits.

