5.2. EFFICACY DATA

The primary analysis and the analyses of all secondary and exploratory efficacy variables will be based on the FAS. In addition to the primary analysis, the primary efficacy variable will also be analysed using the same primary analysis model on the PP set as supportive information.

Primary efficacy parameter

Worsening Heart Failure/all cause death through Day 5

The primary efficacy variable of the study is the time to in-hospital Worsening of Heart Failure (WHF) requiring rescue therapy or all cause death through Day 5 post randomization.

In-hospital worsening of heart failure (WHF) through Day 5 post randomization includes worsening signs and/or symptoms of heart failure that require an intensification of intravenous therapy for heart failure or mechanical ventilation, renal or circulatory support. Such treatment can include the institution or up-titration of IV furosemide, IV nitrates or any other IV medication for heart failure, or institution of mechanical support such as assisted (invasive or non-invasive) ventilation, ultrafiltration, hemodialysis, intra-aortic balloon pump or ventricular assist device, etc. This endpoint also includes patients who die in this 5-day period of any cause before experiencing episode(s) of WHF.

Time to in-hospital WHF/all cause death through Day 5 post randomization will be analysed using survival analysis.

The time to in-hospital WHF/all cause death will be computed as the number of hours from randomization to the earlier of the onset of in-hospital WHF or death plus 1 minute. The onset of in-hospital worsening heart failure through Day 5 will be the start date/time of event

Statistical Analysis Plan

Sponsor: NOVARTIS

Protocol number: CRLX030A3301

reported at the first assessment point at which the investigator reported worsening heart failure; if death occurred, date and time are reported in the dedicated eCRF section. Subjects without an event will be censored at the earlier of the last post-baseline assessment date or 120 hours after randomization. Subjects without any information after baseline (i.e., randomization) will be considered censored at 1 minute.

In case of missing time of in-hospital WHF or death then 00:00 will be imputed.

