	QT/QTcF >460 msec; females only	Female subjects with QT/QTcF ≤460 msec at BL
	QT/QTcF increase from BL >30 msec	Subjects with a non-missing value at BL and post BL
	QT/QTcF increase from BL >60 msec	Subjects with a non-missing value at BL and post BL
PR	PR >200 msec	Subjects with PR ≤200 msec at BL
	PR >220 msec	Subjects with PR ≤220 msec at BL
	PR > 200 msec and change from BL ≥25%	Subjects with PR ≤200 msec at BL
QRS	QRS >110 msec and change from BL ≥25%	Subjects with QRS ≤110 msec at BL
	QRS >120 msec and change from BL ≥25%	Subjects with QRS ≤120 msec at BL
Heart Rate	Heart rate >100 bpm and change from BL ≥25%	Subjects with heart rate ≤100 bpm at BL
	Heart rate <50 bpm and change from BL ≥25%	Subjects with heart rate ≥50 bpm at BL

In addition, shift tables comparing baseline ECG overall interpretation (normal, clinically insignificant abnormality, clinically significant abnormality) with Day 5/discharge ECG overall interpretation (normal, clinically insignificant abnormality, clinically significant abnormality) will be provided by treatment group.

A listing of clinically significant abnormalities in ECG evaluations will be provided.

Echocardiography

Echocardiography is not considered as study related procedures and is performed according to local diagnostic practice.

Overall interpretation will be described by providing the number and proportion of subjects in each category at each assessment time point by treatment group. Percentages will be computed considering patients with non-missing information at each assessment time point.

LV Ejection Fraction (%) will be described by means of summary statistics (i.e., number of observations, mean, standard deviation, median, first and third quartiles, minimum and maximum) at each assessment time point by treatment group.

Systolic blood pressure decrease event

	Statistical Analysis Plan
	Sponsor: NOVARTIS Protocol number: CRLX030A3301

A confirmed systolic blood pressure decrease event (CBPDE) is defined as systolic blood pressure decreases by > 40 mmHg from just before the study drug infusion at baseline but is ≥ 100 mmHg in 2 consecutive measurements 15 minutes apart, or if in 2 consecutive measurements 15 minutes apart, systolic blood pressure reduces to < 100 mmHg, as reported in the "Systolic blood pressure decrease event – vital signs" eCRF.

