For the serelaxin arm only, the number and proportion of patients who experienced a confirmed systolic blood pressure decrease event during study drug administration will be provided. Percentages will be computed considering patients in the analysis population.

The number and proportion of patients who experienced 0, 1, 2, >2 confirmed systolic blood pressure decrease events will be provided together with the number and proportion of patients who experienced asymptomatic/symptomatic events (as recorded on the "Systolic Blood pressure Decrease Event" eCRF page).

The total number of events will be further characterized, showing absolute and relative frequencies of events for the following characteristics:

- Outcome: not recovered/not resolved, recovered/resolved, recovering/resolving, recovered/resolved with sequelae, fatal, unknown
- Action taken with study treatment: none, dose adjusted but not discontinued, permanently discontinued, dose adjusted then permanently discontinued

The category of "dose adjusted then permanently discontinued" for action taken is derived by combining the categories "dose adjusted but not discontinued" and "permanently discontinued" when recorded separately in the eCRF for the same CBPDE.

- Medications or therapies taken: yes or no, if yes type of medication/therapy (fluids/crystalloids, inotropes, vasoressors, circulatory support, mechanical ventilation, other)

Percentages will be computed considering events with non-missing information.

The number and proportion of patients who experienced at least one confirmed systolic blood pressure decrease events will be also presented by outcome, action taken and medications/therapies taken.

The number and proportion of patients who experienced at least one systolic blood pressure decrease events will be also presented by type of event in terms of SBP onset value (mmHg):

- if systolic blood pressure decreased by > 40 mmHg from baseline but was ≥ 100 mmHg;
- if systolic blood pressure reduced to < 100 mmHg.

	<h2 style="margin: 0;">Statistical Analysis Plan</h2>
	Sponsor: NOVARTIS Protocol number: CRLX030A3301

The SBP value (mmHg) at baseline (i.e., at randomization) will be summarized for patients with a confirmed SBP decrease event and for those without a confirmed SBP decrease event.

The following summaries will be presented for patients with a confirmed SBP decrease event:

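### The SAP's comparison of WHF/death by CBPDE (yes/no) ignores which event came first, so it can mislead in either direction and cannot show the impact of a blood-pressure fall

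*SAP*

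**What the plan says.** The last part of the blood-pressure section in SAP 5.3 opens with "To further investigate the impact of CBPDE, the following analyses will be performed". One of the items is "worsening heart failure/all cause death through Day 5 by CBPDE (yes/no"), which is also to be split by whether the dose was reduced, stopped or both. No model, test, landmark or ordering rule is attached.

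The exposure is defined after baseline: "A confirmed systolic blood pressure decrease event (CBPDE) is defined as systolic blood pressure decreases by > 40 mmHg" relative to the value just before infusion with systolic pressure still at least 100 mmHg, or a fall below 100 mmHg, each confirmed 15 minutes later. It is a serelaxin-arm quantity tied to the infusion. The SAP says that the number of patients with a "confirmed systolic blood pressure decrease event during study drug administration will be provided".

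The outcome has a different clock. SAP 5.2 measures it as the "number of hours from randomization to the earlier of the onset of in-hospital WHF or death plus 1 minute", with this censoring rule: "Subjects without an event will be censored at the earlier of the last post-baseline assessment date or 120 hours after randomization".

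Protocol 5.5.9 allows intravenous cardiovascular rescue therapy during the infusion and adds: "The continuation or discontinuation of study drug infusion will then be at the discretion of the investigator". Protocol 5.5.7 warns of additive hypotensive effects in that setting. In SAP 5.3, the definition of IV nitrate intake within 48 hours includes nitrates started or increased because of WHF during the infusion.

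**The concern.** The comparison treats something that happens during follow-up as if it were a group fixed at time zero. Two artefacts follow, and they pull in opposite directions.

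- **Lost opportunity.** A patient who dies or whose infusion is stopped at hour 6 has had little time to have a CBPDE. Such patients collect in the no group and bring their events with them, so pressure falls look protective.
- **Reversed order.** A patient with WHF may receive IV rescue therapy and then have a pressure fall. That WHF is counted in the yes group although the fall came later, so pressure falls look harmful.

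Hypotension is the only safety risk that SAP Table 5.3-1 labels as identified, and this is the SAP's planned comparison of WHF/death by CBPDE. A reader could not tell an artefact from a signal, whichever way the table pointed.

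**Working it through.** The documents give no figure for this analysis, so there is none to reproduce. The check asks what the planned yes/no risk ratio would be if CBPDE had no effect on WHF/death.

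**Inputs from the documents.** The infusion lasts 48 h and the outcome window is 120 h. The five-day WHF/death risk is 6.5%, taken from the serelaxin arm of the earlier phase III trial (Protocol 1.1). With 3183 patients randomized 2:1, the serelaxin arm has 3183 × 2/3 = 2122 patients, and 2122 × 0.065 ≈ 138 events.

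**Assumptions, because the documents give no value.** CBPDE in 10% or 30% of patients, spread evenly over 48 h or concentrated early; 40% or 70% of events in the first 48 h; 10% of events are deaths; early WHF stops the infusion in 0%, 50% or 100% of cases; the CBPDE hazard after rescue therapy is multiplied by 1, 2 or 3.

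**Simulation, 4 million patients per scenario, true ratio 1.**

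| What happens after an early WHF | Yes/no risk ratio |
|---|---|
| Infusion always stops | 0.61–0.93 |
| Infusion stops in half, no effect on BP | 0.77–0.96 |
| Infusion continues, no effect on BP (only death ends the time at risk) | 0.95–0.99 |
| Infusion stops in half, CBPDE hazard ×3 in the rest | 1.01–1.09 |
| Infusion continues, CBPDE hazard ×2 | 1.05–1.30 |
| Infusion continues, CBPDE hazard ×3 | 1.10–1.61 |

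**Hand check of the two extremes.** Take a CBPDE probability of 0.30 at constant hazard, so the cumulative hazard over 48 h is H = −ln 0.70 = 0.3567. Put 70% of events in the first 48 h, evenly spread. Early events are 0.70 × 0.065 = 0.0455 of patients and late events 0.0195. Let q be the chance that a patient with an early event is classed yes; all others have chance 0.30.

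1. *Every early event stops the infusion.* q = 1 − (1 − e^−H)/H = 1 − 0.30/0.3567 = 0.159. Events in the yes group: 0.0455 × 0.159 + 0.0195 × 0.30 = 0.0131. Size of the yes group: 0.0131 + 0.935 × 0.30 = 0.2936. Risks: yes 0.0131/0.2936 = 0.0446; no (0.065 − 0.0131)/0.7064 = 0.0735. Ratio 0.61.
2. *WHF never stops the infusion, hazard ×3 afterwards.* For non-fatal events q = 1 − e^(−3H)(e^(2H) − 1)/(2H) = 1 − 0.343 × 1.0408/0.7133 = 0.500; for deaths 0.159. Average: 0.9 × 0.500 + 0.1 × 0.159 = 0.465. Events in the yes group: 0.0455 × 0.465 + 0.0195 × 0.30 = 0.0270. Size: 0.0270 + 0.2805 = 0.3075. Risks: yes 0.0879; no 0.0380/0.6925 = 0.0548. Ratio 1.60.

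Both agree with the simulation (0.610 and 1.612) to within simulation error.

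**Remedies under the same null.** A landmark at 48 h, restricted to patients free of WHF/death until then, gave 0.98–1.02 throughout. That spread is about what simulation noise produces: the smallest yes groups hold 4,000,000 × 0.10 × 0.065 × 0.30 = 7800 late events, a relative standard error near 1.1%.

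A crude person-time rate ratio, with CBPDE switched on at its onset, was near 1 (0.99–1.01) when 40% of events fell in the first 48 h, which is the same share as 48/120 of the time. With 70% early it fell to 0.78–0.82 for evenly spread CBPDE and 0.93–0.95 for early CBPDE, because unexposed time lies mostly in the high-risk early hours. The time-dependent analysis must therefore condition on time since randomization. A Cox model does this through its risk sets; that argument is structural and was not simulated.

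**The case against.** The strongest objection is that this is one descriptive item in one arm, with no test, among many other displays of hypotension. The SAP also tabulates the outcome of each CBPDE (including fatal), the action taken and therapies given, the haemodynamic course afterwards, the associated adverse events, hypotension by treatment group and a listing of all deaths. Net harm from drug-induced pressure falls would also enter the randomized primary comparison. All of this stands and limits the severity. It does not rescue the item, because the SAP introduces it as a study of impact, and ignoring event order defeats that purpose.

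A reader might go further and infer a built-in bias toward reassurance, with pressure falls made to look harmless or protective. The documents do not support this. It requires early WHF to end the time at risk of a CBPDE, but WHF is non-fatal, rescue therapy is allowed during the infusion and continuing is discretionary. The SAP itself foresees nitrates for WHF during the infusion, a sequence that pushes the ratio above 1. If only death ends the time at risk and rescue has no effect on blood pressure, the bias is small (0.95–0.99).

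A landmark as the main fix also meets a fair objection. It discards events during the infusion, when harm from a pressure fall is most plausible. If counted from randomization, 48 h does not close the exposure window, because Protocol 5.5.5 sets no mandatory interval between randomization and the start of infusion.

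**Conclusion.** The point holds in a limited form. The planned yes/no comparison mixes WHF/death before a CBPDE with WHF/death after it and gives patients unequal opportunity to be classed as exposed, so it cannot show the impact of CBPDE. With no true association the ratio can lie anywhere from about 0.6 to 1.6. That range rests on assumed CBPDE frequency and timing, event timing, infusion-stopping rates and effects of rescue therapy, none of which the documents give. The direction cannot be stated in advance. Severity is minor: this is a secondary safety summary without a stated test, and the primary analysis is unaffected. Label: cheap improvement.

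**What to change.** Amend this item of SAP 5.3 as follows.

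1. In the serelaxin arm, fit a Cox model for time to first WHF/death from randomization, with CBPDE as a time-dependent covariate that switches from 0 to 1 at the first CBPDE. Only WHF/death after the fall is then attributed to it. Handle the split by dose reduction or discontinuation in the same way.
2. Tabulate WHF/death before and after the first CBPDE separately. State how events are ordered when a missing WHF or death time has been imputed as 00:00 under SAP 5.2, since on a shared date that places the event before the CBPDE.
3. Keep the yes/no table and label it descriptive. Put the same label on the adverse-event and concomitant-medication tables by CBPDE.
4. Optionally add a landmark at the end of the infusion window as a sensitivity analysis, with its time origin stated.
5. State that confounding by severity remains under every one of these analyses.

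**Cost.** SAP wording and one extra model. No new data are needed, because SAP 5.3 already derives the time of first CBPDE and SAP 5.2 the time of WHF/death. Intervals will be wide. With about 138 events and no association, the CBPDE-yes group would hold about 14 events if 10% of patients have a CBPDE, or 41 if 30% do, and fewer would follow the fall. Even with all of them, the standard error of the log hazard ratio is roughly √(1/14 + 1/124) = 0.28 or √(1/41 + 1/97) = 0.19. The 95% limits then lie a factor of e^(1.96 × 0.28) ≈ 1.7 or e^(1.96 × 0.19) ≈ 1.4 either side of the estimate.

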3.6 Risks and benefits

The management of AHF remains an area of unmet medical need, even though, therapies are available to improve AHF-related symptoms, no evidence based therapy for the treatment of AHF is currently available.

Previous studies with serelaxin ([Teerlink et al., 2011 and 2013](#)) showed significant improvement in dyspnea and signs and symptoms of congestion, and demonstrated an association of the drug with significant reductions in early worsening heart failure events and length of stay during the index hospitalization, including duration of intensive care. Moreover, pre-specified biomarker changes in previous studies suggest serelaxin therapy has a protective effect on both the heart and kidney.

Serelaxin was generally well tolerated with no notable differences in the overall adverse event profile compared to placebo. Although a decrease in blood pressure can occur due to the vascular mechanism of action of the drug, worse outcomes were not observed. In order to ensure patient safety, the protocol provides instructions for the management of systolic blood pressure (SBP), including close and careful monitoring as well as mandatory dose adjustment or stopping rules.

The risk to subjects in this trial will be minimized by compliance with the eligibility criteria and close clinical monitoring. Since the potential of immunogenicity as a result of repeated intravenous dosing has not yet been fully characterized, those patients who participated in prior serelaxin clinical studies will be excluded. It is also important to note that all patients in

this study will be required to receive standard of care background HF management during hospitalization as well as the period of 30 days following exposure.

Refer to the Investigator's Brochure (IB) for additional information regarding the safety profile of serelaxin.

4 Population

Similarly to the RELAX-AHF study, subjects will be selected among patients who have been admitted with AHF, who have normal to elevated blood pressure (SBP \geq 125 mmHg at the start and at the end of the screening period) and have impaired renal function defined as an eGFR \geq 25 and \leq 75 ml/min/1.73m² at screening (calculated using the sMDRD equation).

The study plans to randomize approximately 3183 patients in approximately 600 study centers mainly in Europe.

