6.6.6 Echocardiography

Echocardiography evaluation is not a mandatory requirement of the protocol; in case the evaluation is performed and the values obtained are available in the source documents, they need to be entered into eCRF. Most recent data up to the last 12 months can be entered.

7 Safety monitoring

All AEs will be collected through Day 5, and all serious adverse events will be collected through Day 14, regardless of suspected causality. After Day 14 only suspected SAEs will be collected and databased.

Specific handling of the Study Endpoint WHF:

WHF events should be recorded not only as an endpoint but systematically as an AE as well. All WHF endpoints should thus be reported as AEs/SAEs in the AE eCRF page.

Non-serious WHF event should be reported through Day 5 and serious (SAE) WHFs should be reported through Day 14. After Day 14, only those study endpoints that qualify for SAEs and are also suspected to be related to the study medication should be reported in the AE eCRF page. It is recommended but not mandatory that the same verbatim should be used for an individual event for both the endpoint reporting and the AE reporting, i.e. "Worsening of Heart Failure".

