7.1 Adverse events

An AE is any untoward medical occurrence (i.e., any unfavorable and unintended sign [including abnormal laboratory findings], symptom or disease) in a subject or clinical investigation subject after providing written informed consent for participation in the study. Therefore, an AE may or may not be temporally or causally associated with the use of a medicinal (investigational) product.

The occurrence of AEs shall be sought by non-directive questioning of the patient at each visit during the study. Adverse events may also be detected when they are volunteered by the patient during or between visits or through physical examination, laboratory test, or other assessments.

Abnormal laboratory values or test results constitute AEs only if they fulfill at least one of the following criteria:

- they induce clinical signs or symptoms,
- they are considered clinically significant,
- they require therapy.

Clinically significant abnormal laboratory values or test results should be identified through a review of values outside of normal ranges/clinically notable ranges, significant changes from baseline or the previous visit, or values which are considered to be non-typical in patients with underlying disease. Investigators have the responsibility for managing the safety of the individual patient and identifying AEs. Alert ranges for lab test abnormalities are included in [Appendix 1](#).

AEs shall be recorded in the Adverse Events eCRF under the signs, symptoms or diagnosis associated with them accompanied by the following information.

- the severity grade
 - mild: usually transient in nature and generally not interfering with normal activities
 - moderate: sufficiently significant to interfere with normal activities
 - severe: prevents normal activities
- its relationship to the investigational treatment (no/yes)
- its duration (start and end dates). If the event is ongoing, an outcome of not recovered/not resolved shall be reported.
- whether it constitutes a SAE
- action taken regarding investigational treatment

- whether other medication or therapies have been taken (concomitant medication/non-drug therapy)
- its outcome (not recovered/not resolved; recovered/resolved; recovering/resolving, recovered/resolved with sequelae; fatal; unknown)

An SAE is any AE (appearance of (or worsening of any pre-existing) undesirable sign(s), symptom(s) or medical conditions(s) which meets any one of the following criteria

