Treatment emergent AEs will be tabulated by System Organ Class (SOC) and Preferred Term (sorted in alphabetical order within each SOC) using the latest MedDRA dictionary, and by System Organ Class, Preferred Term and severity. Absolute and relative frequency of patients who have experienced each type of event will be presented; if the same patient reported more than one occurrence of the same AE with different intensity, the worst reported severity grade for each event for the patient will be used for the analysis. The most frequent treatment emergent AEs will also be tabulated by Preferred Term sorted by descending frequency for AEs with an incidence rate of at least 5% in the serelaxin group.

In addition, treatment emergent adverse events associated with

- worsening heart failure (WHF)/all cause death through Day 5
- confirmed systolic blood pressure decrease event (CBPDE)

will be summarized by system organ class and preferred term. These AEs are determined by taking the answer “Yes” to the questions “Does AE meet the definition of Endpoint?” and “Does AE meet the definition of Systolic Blood Pressure Decrease Event?”, respectively.

Treatment emergent SAEs will be summarized similarly. Treatment emergent SAEs will be summarized by time period of onset, i.e., through Day 5 and through Day 14. Treatment emergent SAEs are defined as those which start after treatment start for serelaxin group, or after randomization for Standard of Care group.

All study-drug-related AEs, AEs with an outcome of death, AEs leading to permanent discontinuation of treatment will be listed with all their details. Time from the treatment start for serelaxin group or from randomization for Standard of Care group, to the AE start/end date, will be also computed. Elapsed days, hours and minutes plus 1 minute will be reported on the listing.

In case of an ongoing event, no days relative to the end of the event will be computed.

In case of missing time of start or end of an event, no relative days will be computed.

Safety risks and events of interest

Adverse events will be also presented according to the search strategies using the latest MedDRA dictionary version available before database lock, as specified in the Case Retrieval Strategy (CRS) defined by Novartis. Adverse events will be characterized as safety risks and as events of interest according to the rules specified in Table 5.3-1 and Table 5.3-2, respectively.

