Safety risks and events of interest through Day 5 and Day 14 will be summarized by treatment group and tabulated by safety risk / events of interest, NMQ, HLGT, SMQ or SOC, and Preferred Term of MedDRA dictionary. Absolute and relative frequency of patients who have experienced each type of event will be presented.

	Statistical Analysis Plan
	Sponsor: NOVARTIS
	Protocol number: CRLX030A3301

Table 5.3-1: MedDRA* search specifications to evaluate safety risks

Safety Risk	Specification
Hypotension (identified)	NMQ 'Hypotension' (Broad) CMQ ' Hemoglobin/ hematocrit transient decrease '
Hemoglobin/ hematocrit transient decrease (potential)	
 • SMQ 'Haemorrhages' (Broad) • HLGT 'Anaemias nonhaemolytic and marrow depression' • SMQ 'Haematopoietic erythropenia' (Broad)
Fetotoxicity and teratogenicity (potential)	SMQ 'Pregnancy and neonatal topics' (Broad)

CMQ: Customized MedDRA query; HLGT: High level group term; NMQ: Novartis MedDRA query; SMQ: Standardized MedDRA query.

* According to MedDRA v19.1. Specifications could possibly change before database lock.

	Statistical Analysis Plan
	Sponsor: NOVARTIS
	Protocol number: CRLX030A3301

Table 5.3-2: MedDRA* search specifications to evaluate events of interest

Event of Interest	Specification
Menorrhagia/Metrorrhagia	HLGT 'Menstrual cycle and uterine bleeding disorders'
Hypokalemia	NMQ 'Hypokalemia' (Broad)
Hypersensitivity/Immunogenicity	CMQ ' Hypersensitivity, Immunogenicity, Cutaneous reactions ': 
 • SMQ 'Hypersensitivity' (Broad) • SMQ 'Angioedema' (Broad) • SMQ 'Anaphylactic reaction' (Broad) • SOC 'Immune system disorders' • HLGT 'Immunology and allergy investigations' • HLGT 'Administration site reactions' • SMQ 'Severe cutaneous adverse reactions' (Broad)
Cardiac failure	SMQ 'Cardiac failure' (Broad) CMQ ' Cardiac arrhythmias/QT prolongation ': 
 • SMQ 'Torsade de pointes/QT prolongation' (Broad) • SMQ 'Cardiac arrhythmias' (Broad)
QT prolongation	
Thromboembolic events	SMQ 'Emolic and thrombotic events' (Broad) CMQ ' Renal impairment ': 
 • SMQ 'Acute renal failure' (Broad) • PT 'Chronic kidney disease'
Renal impairment	
Respiratory failure	SMQ 'Respiratory failure' (Broad)
Hepatotoxicity	SMQ 'Drug related hepatic disorders – comprehensive search' (Broad)
Potential promotion of cancers	SMQ 'Malignancies' (Broad)

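### The adverse-event tables split by confirmed systolic blood pressure decrease event (CBPDE) keep the AE records that are the CBPDE itself, so some rows can show an excess that is built in

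*SAP*

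**What the plan says.** The blood pressure part of SAP 5.3 ends with a short list introduced by "To further investigate the impact of CBPDE, the following analyses will be performed". One item is "adverse events through Day 5 and through Day 14 by CBPDE (yes/no". No exclusion of AE records is stated for that item, and no rule on when an AE must start relative to the fall.

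The adverse-event part of the same section shows that a CBPDE can itself be an AE record. The AE page asks "Does AE meet the definition of Systolic Blood Pressure Decrease Event", and the AEs answered Yes get their own summary by system organ class and preferred term. That summary is additional. It does not remove the records from other tables.

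Three further passages fix the setting:

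- CBPDEs are counted only for patients on serelaxin: "the number and proportion of patients who experienced a confirmed systolic blood pressure decrease event during study drug administration will be provided".
- On collection, Protocol Section 7 says "All AEs will be collected through Day 5, and all serious adverse events will be collected through Day 14, regardless of suspected causality".
- Hypotension is listed in SAP Table 5.3-1 as an identified safety risk, retrieved by "NMQ 'Hypotension' (Broad" query.

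**The concern.** The two groups are defined by whether a CBPDE occurred, and the outcome is whether an AE occurred. If the CBPDE is entered as an AE, the event that puts a patient in the yes group also counts in that group's numerator. Patients in the no group have, by definition, no such record. The any-AE row is then higher in the CBPDE group before any consequence of the fall is considered.

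The same record can reach other rows. It will usually be retrieved by the hypotension query. Protocol 5.5.5 ends the infusion when a fall below 100 mmHg is confirmed, so such a record may also be an AE leading to discontinuation. SAP 5.3 treats AEs with unknown or missing relationship as drug-related, so it may appear there too. The by-CBPDE item does not say which rows will be shown. These are the SAP's standard AE summaries.

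What is at stake is interpretation. Hypotension is the drug's identified risk, and readers will look to this table to judge whether blood pressure falls are followed by other harm.

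**Working it through.** The documents give no figure for this table, so there is nothing to reproduce. The check has two parts.

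**1. Can the overlap occur under the plan as written?**

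- Protocol 7.1 defines an AE to include "any unfavorable and unintended sign [including abnormal laboratory findings], symptom or disease", which is wide enough to cover a fall in blood pressure.
- The AE page has a dedicated question for it, so some such records are expected.
- CBPDEs are counted during the infusion, planned for 48 hours, so they fall inside the Day 5 and Day 14 windows.
- Neither document has a rule that removes the flagged records from the by-CBPDE table.

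So it can occur.

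**2. How large could it be?** Assume the fall has no effect on other AEs. Let

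- p = share of patients with any other AE, equal in both groups (assumed);
- q = share of CBPDE patients whose CBPDE is entered as an AE (assumed), independent of other AEs.

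The CBPDE-no group shows p. The CBPDE-yes group shows p + (1 − p)q. The built-in difference is (1 − p)q.

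With p = 0.35:

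| q | CBPDE yes | CBPDE no | Built-in difference |
|---|---|---|---|
| 0 | 0.35 | 0.35 | 0 |
| 0.10 | 0.35 + 0.65 × 0.10 = 0.415 | 0.35 | 6.5 points |
| 0.25 | 0.35 + 0.65 × 0.25 = 0.5125 | 0.35 | about 16 points |
| 0.50 | 0.35 + 0.65 × 0.50 = 0.675 | 0.35 | 32.5 points |
| 1.00 | 1.00 | 0.35 | 65 points |

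Over p = 0.20 to 0.50 and q = 0.10 to 1, the difference runs from 0.50 × 0.10 = 5 points (ratio 0.55/0.50 = 1.1) to 0.80 × 1 = 80 points (ratio 1.00/0.20 = 5.0).

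The hypotension row is more sensitive because its background is low. With an assumed 1% background and q = 0.10, it reads 0.01 + 0.99 × 0.10 = 10.9% against 1%.

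For scale, Protocol Section 4 says "The study plans to randomize approximately 3183 patients in approximately 600 study centers mainly in Europe". At 2:1 allocation, 3183 × 2/3 = 2122 would be on serelaxin. If 10% to 30% of them had a CBPDE (assumed) and p = 0.35, a nominal two-sided 5% comparison of the any-AE row would be significant with no true impact with probability 0.47 to 0.81 at q = 0.10, and at least 0.99 at q = 0.25. The SAP plans no test here. The figures only show that such a difference could look convincing.

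With the flagged records removed, both groups show p, and the built-in difference is zero for every p and q.

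**The case against.** The strongest reply is that q may be small. Protocol Section 7 orders that worsening heart failure endpoints always be reported as AEs, but no such rule exists for CBPDEs. They have their own eCRF page, which records asymptomatic events, outcome, action taken and therapy. Protocol 7.1 also makes an abnormal test result an AE only if it causes signs or symptoms, is clinically significant, or needs therapy. An investigator who applies that to a blood pressure reading may leave many asymptomatic falls off the AE page. This stands. A reader might infer that every CBPDE is an AE and that the largest differences above are to be expected. The documents do not support that: the flag shows that some are expected, not how many.

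The list is also descriptive. It includes baseline characteristics by CBPDE, which cannot be consequences of the fall, and it states no test, whereas the nearby nitrate comparison does. This stands too and keeps the point minor.

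A reader might further infer that the table can tell nothing about the effect of a fall. That goes too far. In a layout by preferred term, the overlap sits in the blood pressure rows and the totals, and rows for unrelated terms are not inflated by this route. Only serious AEs are collected after Day 5 (only suspected ones after Day 14), so if the Day 14 table is restricted to them, the artefact there is limited to serious CBPDEs.

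The separate summary of flagged AEs does not answer the point. It shows the records but leaves them in the by-CBPDE table.

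Finally, because AEs that began before the fall also count in the CBPDE group, it is tempting to drop them from that group. Doing so in one group only would shorten its counting window while the other kept every AE from the start of treatment. That would bias the comparison towards making the fall look harmless.

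**Conclusion.** The point holds as a minor matter of reporting. As written, the plan lets the event that defines the CBPDE group count among that group's adverse events, in a table meant to examine the event's impact. The excess depends on a share that the documents do not give. It is zero if no CBPDE is an AE record. At an assumed 35% background it is 6.5, about 16 and 32.5 points for shares of 10%, 25% and 50%. It is confined to the any-AE total, the hypotension and blood pressure rows, and any drug-related or discontinuation rows shown. The primary analysis and its error rate are untouched.

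**What to change.** In SAP 5.3, under the analyses of CBPDE impact, state that the AE-by-CBPDE tables will be shown twice: with all AE records, and without those answered Yes to the Systolic Blood Pressure Decrease Event question. Label both as descriptive and within the serelaxin arm, since the list does not repeat that restriction. State whether the Day 14 table covers serious AEs only.

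Do not drop AEs that preceded the fall in the CBPDE group alone. If timing is to be addressed, use a common start for both groups, for example AEs with onset after a 48-hour landmark, by which time the infusion must have ended (SAP 2.4) and CBPDE status is settled. This gives up AEs that follow a fall but begin within the first 48 hours.

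The cost is one extra table version, a filter on an existing eCRF field, and a few lines of SAP text. The excluded version needs one caution. It removes later flagged episodes in patients with more than one CBPDE, and it thins the hypotension row in the CBPDE group while unflagged hypotension AEs stay in the other group. That row should be read beside the SAP's separate summary of flagged AEs.
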